## **Study Design**

### **Research Design**

The research strategy will employ a prospective, mixed methods implementation science design based on the Reach, Effectiveness, Adoption, Implementation, and Maintenance (RE-AIM) framework.

Reach will include the number of patients in the community that are offered and undergo cancer screening. Effectiveness will be determined by comparison of monthly breast, lung, and prostate cancer screening referral uptake to baseline. Adoption will be evaluated by the number of patients with positive screens that are referred for screening and for treatment. Implementation will occur via the cyclical improvement triad approach that includes repeated evaluation and modification to ensure that barriers to care are addressed. Maintenance and sustainability will be supported by the return on investment by early cancer detection and treatment.

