### Inclusion Criteria

The inclusion criteria for patients will be the following:

1. Adult aged 18 or older
2. Seeking care at a CRS or emergency department
3. Meets criteria for lung, breast, and/or prostate cancer screening, as outlined below:
  - a. Lung cancer: Adults aged 50 to 80 years who have a 20 pack-year smoking history and currently smoke or have quit within the past 15 years
  - b. Breast cancer: Women aged 40 to 74 years
  - c. Prostate cancer: Men aged 55 to 69 years
4. Receives a positive screening result for lung, breast, and/or prostate cancer at a study site

The inclusion criteria for stakeholders will be the following:

1. Speaks English or Spanish through study interpreters
2. Able to attend 75% or more of scheduled meetings
3. Must be key individuals providing critical services to address food insecurity, employment assistance, government support, mental and physical health, and health education within identified Community Resource Spots, emergency departments, and urgent care centers.

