## Study Duration

The project is projected to begin on August 1, 2025. Study subjects will be enrolled for 9 months. Participants will remain active in the study until they have received a definitive diagnosis and treatment plan or declined further care. The study activities, including data analysis, will be completed within 12 months from the start date.

The implementation plan that details study activities and timelines will be developed according to current best practice for evaluating effectiveness and will be informed by input from the stakeholder group at each site. The implementation plan is as follows:

- Month 1: Finalize key stakeholders at each site and initiate monthly implementation meetings with study team and including stakeholders as needed, collect baseline data and initiate ongoing data gathering (i.e., lung, breast, prostate cancer screening knowledge, attitudes, and practices, cancer screening barriers and facilitators), establish care navigation and communication processes and launch project.
- Month 2: Data collection and monitoring of all sites, implementation meetings.
- Month 3: Data collection and monitoring of all sites, implementation meetings.
- Month 4: Data collection and monitoring, implementation cycle 1 adjustments, stakeholder meetings for data sharing and plans, patient study enrollment.
- Months 5-7: Continue monthly implementation meetings, data collection, study enrollment, data-driven process improvement.
- Month 8: Stakeholder meetings, implementation cycle 2 adjustments.

- Months 9-10: Continue monthly implementation meetings, data collection, study enrollment, process improvement.
- Month 11: Final data collection and analyses.
- Month 12: Final reporting, stakeholder meeting and sustainability plan development.

	FL CANCER FUND PROJECT PERIOD MONTHS											
	1	2	3	4	5	6	7	8	9	10	11	12
Implementation plan finalized	X											
Implementation plan socialized	X											
Stakeholder meeting (x # sites)	SM	SM	SM	SM	SM	SM	SM	SM	SM	SM	SM	SM
Active Implementation period	Zipcode 1											
	MONITORING/ADJUSTMENTS AS NEEDED											
	Zipcodes 2 & 3											
Implementation Iteration cycles				Cycle 1					Cycle 2			
Data collection	BASELINE	X	X	X	X	X	X	X	X	X	X	FINAL
Interview themes + Quantitative data review		X	X	X	X	X	X	X	X	X	X	X
Reporting requirements			PR due			PR due			PR due			FR due

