## Study Outcome Measures (Endpoints)

### Dashboard and Records

There will be an information architect on the study team who will build and maintain a dashboard to track the project metrics. These metrics can be categorized into the RE-AIM model dimensions of Reach, Effectiveness, Adoption, Implementation, and Maintenance, which are outlined below.

- **Reach**
  - Percentage and characteristics of patients included or excluded
  - Percentage of patients who receive screening at point of care or referral
  - Characteristics of participants and non-participants
- **Effectiveness**
  - All positive screens referred for confirmatory diagnostics
  - Measure of screening rates with comparison to the goals set forth in Healthy People 2030 (HP2030)
    - Increase the proportion of adults aged 55 to 80 years (30-pack-year smoking history, currently smoking or quit in the past 15 years) who receive a lung cancer screening to meet the HP2030 target of 7.5%
    - Increase the proportion of females aged 40 to 74 years who receive biennial screening mammography to meet the HP2030 target of 80.3%
    - Increase the proportion of men ages 55 to 69 years that discuss the possible benefits and harms of prostate-specific antigen (PSA) screening with their health care provider and make an individualized decision about whether to get screened
- **Adoption**
  - Percentage of providers who receive education on screening guidelines for breast, lung, and prostate cancer
  - Uptake of cancer screening in the field by number of providers

- Percentage of provider staff that engaged with navigation program
- **Implementation**
  - Number of patients referred to navigation program
  - Rates of 1) low dose CT lung cancer screens 2) biennial screening mammography, and 3) prostate specific antigen (PSA)
  - For those who have a positive screen: 1) time to referral, 2) time and barriers/facilitators to diagnosis 3) uptake of treatment, and 4) number screened for clinical trials
- **Maintenance**
  - Measure of primary outcomes at 3 months post-intervention with progress towards Healthy People 2030 goals
  - Short-term attrition rate
  - Differential rates by patient characteristics

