### **Statistical Analysis Plan**

#### **Primary Objective Analysis**

Patient-reported demographic characteristics will be analyzed using descriptive statistics associated with the **Reach** aim. To address the **Effectiveness** aim pre- and post-intervention barriers data and patient-reported outcomes will be analyzed using univariate, bivariate, and repeated measures analyses. Referral data will be

descriptively evaluated based on percent increase/decrease across the intervention. Qualitative data will be analyzed to determine the extent to which the **Adoption** aim was met. Analyses of the fidelity of the intervention, including timeliness and consistency will be documented as part of the **Implementation** aim. Finally, process-level descriptions, including the summation of monthly team meetings and direct communications with the Implementation Scientist of the community-focused multi-disciplinary navigation intervention will be used to assess the **Maintenance** aim.

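### Adoption and Maintenance are described inconsistently across the protocol, their planned analysis uses none of their listed endpoints, and the 3-month Maintenance measure does not appear to fit the 12-month schedule

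*Protocol*

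**What the plan says.** The primary objective is to evaluate the outreach programme with the RE-AIM framework, so all five dimensions belong to it. Three sections of the protocol describe how Adoption and Maintenance are assessed.

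**Adoption**
- Research Design: "Adoption will be evaluated by the number of patients with positive screens that are referred for screening and for treatment".
- Dashboard and Records lists three provider-level measures. The first is "Percentage of providers who receive education on screening guidelines for breast, lung, and prostate cancer". The others are field screening uptake by number of providers, and the share of provider staff who engaged with navigation.
- Primary Objective Analysis: "Qualitative data will be analyzed to determine the extent to which the" Adoption aim was met.

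**Maintenance**
- Research Design: "Maintenance and sustainability will be supported by the return on investment by early cancer detection and treatment".
- Dashboard and Records lists "Measure of primary outcomes at 3 months post-intervention with progress towards Healthy People 2030 goals", together with a short-term attrition rate and rates broken down by patient characteristics.
- Primary Objective Analysis assesses it from "process-level descriptions, including the summation of monthly team meetings and direct communications with the Implementation Scientist".

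**Schedule**
- The Study Duration text for Months 9 and 10 reads "Continue monthly implementation meetings, data collection, study enrollment, process improvement". It places final data collection in Month 11 and ends all activity, analysis included, within 12 months. The table in the same section marks the final data point in the Month 12 column.

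**The concern.** A protocol may leave the detail of tabulation to a later plan. Here, however, Primary Objective Analysis does say what will decide each dimension, and for these two it names material other than the protocol's own endpoints.

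For Adoption the unit changes from patients, to providers, to interview and observation themes. Qualitative material can explain why providers did or did not take part, but it cannot produce a percentage of providers. For Maintenance, a record of meetings and communications cannot show whether screening rates held up.

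If the plan is followed, the report can state conclusions on both dimensions without the provider percentages, attrition or later rates listed for them. With differing descriptions on file, the team could also choose after the fact which one to report. Separately, a Maintenance measure that falls after data collection ends would either go missing or be replaced by something else under the same label.

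**Working it through.** No sample size, power or error rate bears on this point. The check is a comparison of sections and one piece of calendar arithmetic.

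**Step 1. Listed endpoints against the analysis sentences**

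| Dimension | Endpoint in Dashboard and Records | Named in that dimension's sentence in Primary Objective Analysis? |
|---|---|---|
| Adoption | Percentage of providers educated | No |
| Adoption | Field screening uptake by number of providers | No |
| Adoption | Percentage of provider staff engaged with navigation | No |
| Maintenance | Primary outcomes 3 months post-intervention | No |
| Maintenance | Short-term attrition | No |
| Maintenance | Differential rates by patient characteristics | No |

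Result: Adoption 0 of 3, Maintenance 0 of 3, so 0 of 6 in all.

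**Step 2. Number of differing descriptions**

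Adoption has three: patient referrals, provider measures and qualitative data. Maintenance has two that clearly differ: listed rates and process descriptions. The return-on-investment sentence says what will sustain the programme more than how Maintenance is measured, and no cost measure appears among the study outcome measures. It is only loosely a third description.

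**Step 3. Where referrals sit**

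Dashboard and Records puts referral of positive screens for confirmatory diagnostics under Effectiveness. It puts the number referred to navigation and time to referral under Implementation. It lists no referral measure under Adoption, so the Research Design wording for Adoption conflicts with the endpoint list even before the analysis section is read.

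**Step 4. Whether the 3-month measure fits**

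Let E be the last month of the intervention. The measure falls in month E + 3.

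| E | E + 3 | Fits data in Month 11? | Fits data in Month 12? |
|---|---|---|---|
| 8 | 11 | Yes | Yes |
| 9 | 12 | No | Yes |
| 10 | 13 | No | No |

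Equivalently, the latest workable E is 11 − 3 = 8 or 12 − 3 = 9. The protocol does not state E. Taking E = 10 is an assumption drawn from the Study Duration text, which continues implementation meetings, enrolment and process improvement through Month 10. The same text places cycle 2 adjustments in Month 8, so an end by Month 8 would leave no intervention months after those adjustments. The table row for the active implementation period has lost its month spans, so a staggered end by zip code cannot be ruled out.

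**Step 5. Whether another reading of 3 months rescues it**

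Patient surveys are repeated at 3 months, but that is a per-patient interval. The Maintenance endpoint is tied to the Healthy People 2030 goals, which the protocol states as population proportions screened or counselled. The survey interval does not supply them. The protocol also never says which outcomes are the primary outcomes to be measured again.

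**The case against.** The strongest reply is that nothing is lost. The dashboard is built to track every listed metric by dimension. These are simple counts and percentages in a single-arm descriptive evaluation, and their tabulation could sit in an analysis plan not shown here. Referral data are evaluated descriptively as percent change, which partly reaches the Research Design version of Adoption. Stakeholder interviews ask about staff participation under Adoption. Withdrawn participants are counted in the flowchart, which bears on attrition.

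Much of this is fair, and it rules out several stronger readings:

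- A reader might infer that the two dimensions go unanswered. They do not: each has a stated assessment, only not one that uses its listed endpoints.
- A reader might infer that the 3-month measure is impossible. That needs an intervention end date that the protocol does not give.
- A reader might infer a favourable bias, because stakeholders must be "Able to attend 75% or more of scheduled meetings" and so are selected for engagement. But the qualitative data also come from patient interviews and field observations, patients face no attendance rule, and the stakeholder questions ask about barriers. Neither the direction nor the size of any bias is established.
- A reader might infer that results could not be compared with other RE-AIM evaluations. Nothing in the protocol bears on this.

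What does not stand is the claim that tracking settles the matter. Tracking a metric is not the same as using it to judge an aim, and the analysis section names other material for that. The section that applies qualitative analysis to every dimension does so to explain influential factors under the secondary objective.

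**Conclusion.** The point holds as an internal contradiction in the protocol. Its three descriptions of Adoption differ, at least two descriptions of Maintenance differ, and none of the six endpoints listed for these dimensions appears in the sentences that analyse them. This rests on the text alone and needs no assumption.

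The timing problem is likely but conditional. On the implied end in Month 10, the measure falls in Month 13, two months after final data collection in Month 11 and one month after the study ends. It is workable only if the intervention stops by Month 8 or Month 9, depending on which month holds the final data.

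This should be corrected, but it does not undermine the study: the data are already planned, and the other three dimensions are not touched by this point.

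**What to change.** 1. Use one definition per dimension in Research Design, Dashboard and Records, and Primary Objective Analysis.
2. **Adoption:** in Primary Objective Analysis, report the three provider measures descriptively from the dashboard, with numerators and denominators, by site where numbers allow (20 sites are planned). Keep the qualitative data to explain them. A split by cancer type is not needed, since staff engagement with navigation is not specific to one cancer.
3. **Referrals:** align the Research Design count with Effectiveness and Implementation, where the endpoint list already places referrals.
4. **Maintenance:** report short-term attrition, differential rates, and the screening and referral rates. Say which outcomes are the primary outcomes. Keep meeting summaries and communications as supporting material.
5. **Timing:** state in Study Duration when the intervention ends. If 3 months of later data cannot be collected within the study, compare rates in the last months of data with earlier months, label this late-implementation performance, and make no 3-month post-intervention claim.

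The cost is wording in four sections and some descriptive tables from counts already tracked. No new participants or visits are needed. The downside, if the fallback in item 5 is used, is a weaker Maintenance claim.

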### Secondary Objective Analysis

Qualitative analysis will be utilized to explore and explain influential factors for each RE-AIM dimension (Holtrop, Rabin, & Glasgow, 2018). Transcripts from interviews, field observations, and stakeholder meetings will be analyzed utilizing thematic analysis to explore factors that influence uptake patterns across patients, providers, navigators, and implementation sites (Braun & Clarke, 2006). Prompt turnaround of qualitative data analyses will inform timely action plans with stakeholders (Kowalski et al., 2024; Lewinski et al., 2021).

## Potential Risks and Benefits

### Potential Benefits

There are no direct benefits of participation.

### Potential Risks

There are no risks involved beyond what would reasonably be encountered in everyday life. It is possible that participants may experience the following during the study:

- Loss of privacy as a result of a breach of confidentiality
- Undue stress related to the questionnaires which ask about physical and emotional well-being

### Mitigation of Risks

Participants will be informed that measures are in place to prevent the loss of privacy and to protect data, such as deidentification of responses and the use of HIPAA-compliant electronic data capture system. In addition, the organization has safeguards in place to secure information technology. Participants will be given hotline numbers for mental health support if needed.

### Provisions to Protect the Privacy Interest of Subjects

The protection of study participants will be accomplished by adhering to ethical and legal guidelines. All policies for the protection of human subjects mandated by the AdventHealth IRB and U.S. Federal Guidelines for conducting research with human subjects will be followed. Subjects will be assigned unique identifiers for study-related records. Precautions will be taken to make sure that only authorized individuals will access subject research records. The collection of sensitive information about subjects will be limited to the minimum necessary to achieve the aims of the research so that no unneeded sensitive information will be collected.

## **Early Withdrawal of Subjects**

### **Investigator Withdrawal of Subjects**

Participants may be withdrawn from the study if they are unable or unwilling to comply with the study protocol.

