### **Consent Process**

The researchers will follow SOP CW AHC 216 Informed Consent Process and Written Documentation of Informed Consent. Also, the researchers will follow SOP CW AHC 249 Remote and Electronic Methods for Conducting Informed Consent in Non-Exempt Research.

**For Patients:** Upon referral for definitive diagnosis based on their cancer screening results, patients will be contacted by a study team member for informed consent for survey completion, interviews and electronic health record access to monitor outcomes. All consent forms will be completed on paper or electronically via REDCap on a tablet device provided by the study team.

**For Stakeholders:** Study team members will contact community stakeholders in person, or via phone or email to re-explain the study and obtain consent. Consent forms may be completed on paper or electronically via REDCap.

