**Non-English Speaking Subjects**

Check here to confirm you will follow HRP-804 INVESTIGATOR GUIDANCE  
Short Form Consent Process

Consent forms and all study materials will be translated into Spanish for both Spanish-speaking patients and stakeholders.

For patients and stakeholders that speak Spanish as a primary/preferred language, the study team will ensure that a Spanish-speaking research team member is in place to navigate the consent process, study activities, provide directions, and guidance on next steps.

For patients:

Spanish-speaking participants will be included only in surveys that are validated in English and Spanish. Spanish-speaking participants will be eligible for focus groups and interviews with a Spanish-speaking team member.

Those patients who do not speak English or Spanish as a primary language will be consented appropriately using a consent form that is fully translated and provided to the participant as soon as possible. These individuals will be eligible for medical record tracking for follow-up but will not participate in surveys or interviews.

For all non-English speakers, short form consents will be utilized using medical translators until regulatory requirements dictate translation of consent.

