Medical records will be followed until definitive diagnosis and treatment disposition to track the patients' progress through the cancer care continuum. If diagnosis is negative, then interaction with the medical record ends upon confirmation of negative test. If diagnosis is positive, then the medical record is followed monthly to determine: diagnostic codes, treatment decisions, treatment course, and treatment outcomes. This may include labs, demographics, medication histories, referrals, outpatient visit notes, inpatient progress notes, and imaging.

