### **Data Collection and Follow-up for Withdrawn Subjects**

Participants who are withdrawn from the study for any reason will have their previous data included in summary reports (i.e., baseline characteristics) and pre-post comparison analyses up to the point of withdrawal unless they specifically request that their data be excluded from future use. They will be counted in the participant flowchart. A study team member will contact participants who do not complete the entire research study to find out the reason(s) to guide future program development and improvement.

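### The withdrawal rules do not separate stopping surveys or interviews from ending medical-record follow-up, so diagnosis and treatment outcomes can be cut short, possibly selectively

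*Protocol*

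**What the plan says.** Four parts of the protocol bear on this point.

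- **Withdrawal by the investigator** (Investigator Withdrawal of Subjects): "Participants may be withdrawn from the study if they are unable or unwilling to comply with the study protocol". The rule is discretionary and does not say which activity the non-compliance must concern.
- **Data after withdrawal** (Data Collection and Follow-up for Withdrawn Subjects): earlier data stay in the summary reports and in "pre-post comparison analyses up to the point of withdrawal unless they specifically request that their data be excluded from future use". Withdrawn patients are counted in the flowchart. The only later contact foreseen is to learn why a participant did not complete the study.
- **Planned follow-up**: Study Duration states that "Participants will remain active in the study until they have received a definitive diagnosis and treatment plan or declined further care". Dashboard and Records states that "Medical records will be followed until definitive diagnosis and treatment disposition to track the patients' progress through the cancer care continuum".
- **Scope of participation**: Consent Process describes one "informed consent for survey completion, interviews and electronic health record access to monitor outcomes". For patients who speak neither English nor Spanish, Non-English Speaking Subjects separates these parts: "These individuals will be eligible for medical record tracking for follow-up but will not participate in surveys or interviews".

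**The concern.** Surveys and interviews need the patient's cooperation. Following the medical record mostly does not. The withdrawal sections treat the two as one package, so a patient who will not do the first may also be removed from the second.

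The outcomes exposed are those that develop after enrolment: time to diagnosis, uptake of treatment and the number screened for clinical trials, all listed under Implementation in the outcome measures. The first secondary goal, comparing adults who accept with those who decline follow-up diagnosis, treatment and trial screening, depends on the same follow-up. The background and intervention sections describe distrust, poor access to primary care and episodic care-seeking. It is plausible, though not shown, that patients who drop study contacts are also more likely to delay or decline diagnostics. If so, the missing follow-up would not be a random part of the sample. Records that were never followed cannot be recovered by a later analysis plan, so the point belongs in the protocol.

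**Working it through.** The protocol gives no withdrawal rate, power calculation or expected uptake, so there is no figure to reproduce. The check is a comparison of sections, followed by an illustration on assumed rates.

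**Comparison of sections**

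1. *What can a patient fail to comply with?* Study Visits lists, after consent, baseline surveys, a first interview, 3-month surveys and optional follow-up interviews, and nothing else. Recruitment of Patients describes navigation as standard of care, unaffected by study involvement. Non-compliance would thus mostly concern surveys, and perhaps the first interview.
2. *What follows from withdrawal?* The section headed for data collection and follow-up of withdrawn subjects covers earlier data ("pre-post comparison analyses up to the point of withdrawal") and contact about reasons. It does not provide for further record tracking, and does not expressly forbid it.
3. *How far was follow-up meant to run?* To definitive diagnosis and treatment disposition, with monthly record review if the diagnosis is positive.
4. *Is record-only participation acceptable in this study?* Yes. It is already the arrangement for one language group.

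Steps 1 and 2 allow follow-up to end earlier than step 3 intends, for a reason that step 4 shows need not end it.

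**Illustration (all rates assumed)**

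Input from the protocol: 200 subjects at all sites combined. Assumed: share withdrawn *w* of 5% to 30%; treatment uptake of 80% in retained patients (*p_r*) and 40% to 60% in withdrawn patients (*p_w*); withdrawn patients leave the denominator.

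- Patients without complete follow-up = 200 × *w*
- Overstatement of uptake = *p_r* − [(1 − *w*) × *p_r* + *w* × *p_w*] = *w* × (*p_r* − *p_w*)
- Worst-case bounds around an observed 80% = 0.80 × (1 − *w*) to 0.80 × (1 − *w*) + *w*

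| *w* | Patients | Overstatement if *p_w* = 60% | Overstatement if *p_w* = 40% | Bounds |
|---|---|---|---|---|
| 5% | 10 | 1 point | 2 points | 76–81% |
| 10% | 20 | 2 points | 4 points | 72–82% |
| 20% | 40 | 4 points | 8 points | 64–84% |
| 30% | 60 | 6 points | 12 points | 56–86% |

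For example, with *w* = 20% and *p_w* = 40%: 0.20 × (0.80 − 0.40) = 0.08. If *p_w* = *p_r*, the overstatement is 0 for every *w*.

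**The case against.** The strongest reply is that this is an ambiguity, not a stated loss of data. Much of that reply stands.

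- The rule says participants may be withdrawn, and names neither surveys nor interviews. Interviews are by invitation and the follow-up ones are optional, so refusing one is not clearly non-compliance.
- The section on withdrawn subjects governs the use of earlier data. That record tracking stops is its natural reading, but is not written.
- Declining further care is a planned end of participation under Study Duration. A decline documented before withdrawal is kept.
- The Enrollment Log already holds withdrawal and its reason. Short-term attrition, differential rates by patient characteristics and characteristics of non-participants are planned metrics. These make selective loss visible, though they do not restore the missing outcomes.
- The consent form is not available here and may already separate the two kinds of withdrawal.
- Denominators and missing-data handling may be set in an analysis plan that is not shown.
- Some diagnostics may take place at external clinics, where access to records is not established, so record follow-up would not recover everything.

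A reader might infer that follow-up is in fact lost in the hardest-to-reach patients, or that the rule removes the decliners whom the first secondary goal needs. The protocol supports neither. It does not say who would be withdrawn or how many, and it treats a decline of care as an endpoint, not as a ground for withdrawal.

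What the reply does not answer is that discretion without criteria, over a planned total of 20 sites, can be applied differently from site to site, and that staff who follow the text have no stated basis for continuing record follow-up after withdrawal.

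**Conclusion.** The point holds as a gap in the withdrawal rules. They do not distinguish stopping surveys or interviews from ending record follow-up, and they can therefore cut short time-to-diagnosis, treatment-uptake and trial-screening data before the patient's decision is recorded. This sits badly with the planned length of follow-up and with the record-only arrangement already accepted for one group.

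The size of any bias cannot be derived from the protocol. The tabulated range of 1 to 12 points rests wholly on assumed withdrawal and uptake rates and on withdrawn patients leaving the denominator. Bias is zero if outcomes do not differ between withdrawn and retained patients; what then remains is incomplete follow-up and some loss of precision. The change is worth making because the loss could not be repaired at the analysis stage and the remedy is small.

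**What to change.** Amend Investigator Withdrawal of Subjects and Data Collection and Follow-up for Withdrawn Subjects to state that:

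1. missed or refused surveys or interviews end those activities only;
2. medical-record follow-up, as described under Dashboard and Records, continues unless the participant withdraws consent for record access;
3. the level of withdrawal (surveys, interviews, record access) is entered in the Enrollment Log beside the reason already kept there.

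The participant's right to withdraw fully at any time stays as it is. The cost is a few sentences in the protocol, one more field in the log, a few more monthly record checks, and matching wording in the consent form if it is not already there.
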